6.7.1 Stratum 1 (12 hour follow-up)

During the course of the study day, it is particularly important for site teams to check the patency of PK catheters. If a catheter is determined to be compromised in anyway, another catheter may be placed in the same arm as the original catheter utilizing a different vein.

PK draws will be drawn via the venous catheter at the following timepoints:

- PK draw in K_2 EDTA tube at 5 minutes (±2 minute)
- PK draw in K_2 EDTA tube at 15 minutes (±2 minute)
- PK draw in K_2 EDTA tube at 30 minutes (± 2 minutes)
- PK draw in K_2 EDTA tube at 60 minutes (±2 minutes)
- PK draw in K_2 EDTA tube at 90 minutes (±2 minute)
- Vital sign collection at 90 minutes (±5 minutes)
- PK draw in K₂ EDTA tube at 120 minutes (±5 minutes)
- PK draw in K_2 EDTA tube at 180 minutes (±5 minutes)
- PK draw in K₂ EDTA tube at 240 minutes (±5 minutes)
- Vital sign collection at 250 minutes (±5 minutes)
- PK draw in K₂ EDTA tube at 300 minutes (±5 minutes)
- PK draw in K_2 EDTA tube at 360 minutes (±5 minutes)
- PK draw in K_2 EDTA tube at 480 minutes (±5 minutes)
- Vital sign collection at 500 minutes (±5 minutes)
- PK draw in K_2 EDTA tube at 600 minutes (±5 minutes)
- Perform a 12 lead ECG at 700 minutes (±5 minutes)
- Vital sign collection (includes temperature) at 710 minutes (±5 minutes)
- PK draw in K₂ EDTA tube at 720 minutes (±5 minutes)

- Obtain laboratory tests including chemistry, hematology, and urinalysis (See Section 7.1.2.6 and Table 3) at 725 minutes (±5 minutes)
- At the conclusion of TGFR measurements (when tGFR is reported on the monitor), the sensor may be removed
- Adverse events will be collected based on subject reports and medical team observations

6.8 Stratum 2 (24 hour follow-up)

PK draws will be drawn via the venous catheter at the following timepoints:

- PK draw in K_2 EDTA tube at 5 minutes (±2 minute)
- PK draw in K_2 EDTA tube at 15 minutes (±2 minutes)
- PK draw in K_2 EDTA tube at 30 minutes (± 2 minutes)
- PK draw in K_2 EDTA tube at 60 minutes (± 2 minutes)
- PK draw in K_2 EDTA tube at 90 minutes (±2 minute)
- Vital sign collection at 90 minutes (±5 minutes)
- PK draw in K_2 EDTA tube at 120 minutes (±5 minutes)
- PK draw in K_2 EDTA tube at 180 minutes (±5 minutes)
- PK draw in K_2 EDTA tube at 240 minutes (±5 minutes)
- Vital sign collection at 250 minutes (±5 minutes)
- PK draw in K₂ EDTA tube at 300 minutes (±5 minutes)
- PK draw in K_2 EDTA tube at 360 minutes (±5 minutes)
- PK draw in K_2 EDTA tube at 480 minutes (± 5 minutes)
- Vital sign collection at 500 minutes (±5 minutes)
- PK draw in K_2 EDTA tube at 600 minutes (±5 minutes)
- Perform a 12 lead ECG at 700 minutes (±5 minutes)
- Vital sign collection (includes temperature) at 710 minutes (±5 minutes)
- PK draw in K_2 EDTA tube at 720 minutes (±5 minutes)

- Obtain laboratory tests including chemistry, hematology, and urinalysis (See Section 7.1.2.6 and Table 3) at 725 minutes (±5 minutes)
- PK draw in K_2 EDTA tube at 960 minutes (±5 minutes)
- PK draw in K_2 EDTA tube at 1200 minutes (± 5 minute)
- PK draw in K_2 EDTA tube at 1440 minutes (± 5 minutes)
- Vital sign collection at 1450 minutes (±5 minutes)
- At the conclusion of TGFR measurements (when an tGFR is reported on the monitor), the sensor may be removed.
- Adverse events will be collected based on subject reports and medical team observations
- Subjects may be discharged from the study center

6.9 Follow-up Visit

Subjects will return for a safety follow-up visit approximately 7 +/-3 days after the dosing visit. The following assessments will be performed

- Perform a full or limited physical exam and collect vital signs including temperature (Sections 7.1.2.7 and 7.1.2.8)
- Obtain laboratory tests including chemistry, hematology, and urinalysis (Section 7.1.2.6 and Table 3).
- Record concomitant medications
- Collect adverse events; review ongoing AEs and document resolution (when applicable)

6.10 Early Withdrawal / Unscheduled Visits

Any subject that withdraws from the study early for any reason, or who needs to have an unscheduled visit performed to assess a safety issue, will have the following assessments performed:

- Obtain laboratory tests including chemistry, hematology, and urinalysis profile (Section 7.1.2.6 and Table 3).
- Perform a full or limited physical exam and collect vital signs (Sections 7.1.2.7 and 7.1.2.8)
- Record concomitant medications

- Collect adverse events; review ongoing AEs and document resolution (when applicable)
- Record withdrawal date and reason for withdrawal, if appropriate

6.11 Repeat Subjects

Subjects may be re-enrolled in the protocol in the following situations (and if no documented safety concerns regarding exposure to the investigational device or drug):

- When a dose extravasation has occurred
- When there is a device malfunction (sensor falling off during the monitoring period and before a tGFR has been reported)
- Back-up subjects who were not dosed

Stratum 1 subjects must have a minimum of a 3-day wash-out from prior exposure of MB-102 before receiving another dose. Stratum 2 subjects must have a minimum of a 7-day wash-out from prior exposure of MB-102 before receiving another dose

In some cases, the screening visit (if outside the 21-day window) may need to be repeated. Repeat subjects will maintain the same subject ID.

Subjects can be in the study a maximum of two times and only when the above situations have occurred.

7 Efficacy and Safety Variables

7.1 Efficacy and Safety Measurements Assessed and Flow Chart

 Table 2 shows the planned study assessments.

7.1.1 Efficacy Assessments

This pivotal study is not designed to address treatment efficacy rather it is to evaluate the use of MB-102 and the MediBeacon[®] Transdermal GFR Measurement System to provide a point of care (POC) means to collect GFR data. The specific endpoints related to calculation of GFR are discussed in Section 9.

7.1.2 Safety Assessments

Safety will be monitored by the assessments described below as well as the collection of AEs at every visit after screening. Planned safety assessments are detailed in the MediBeacon[®] Transdermal GFR Measurement System Study Schedule (**Table 2**). The investigators or site staff will be responsible for monitoring the safety of subjects who have entered this study and will be responsible for detecting, documenting and reporting events that meet the definition of an adverse event (AE) or serious adverse event (SAE). Significant findings that were noted to be

present at or prior to dosing must be included in the relevant medical history page of the eCRF. Significant new findings that begin or worsen after dosing must be recorded on the AE page of the eCRF. Subjects should be followed until the event is resolved or stabilized. AEs are collected from the time of initial sensor placement until the completion of the follow-up visit.

7.1.2.1 Adverse Events

Adverse Event Definition

An adverse event is defined as any untoward medical occurrence, unintended disease or injury, or untoward clinical signs (including abnormal laboratory findings) in subjects, temporally associated with the use of a medicinal product, whether or not related to the investigational medical device or drug.

An unanticipated adverse device effect (UADE) is any serious adverse effect on health or safety, any life-threatening problem or death caused by, or associated with a device, if that effect, problem, or death was not previously identified in nature, severity, or degree of incidence in the application; or any other unanticipated serious problem associated with a device that relates to the rights, safety, or welfare of subjects. For the purposes of this trial, the device is the MediBeacon[®] Transdermal GFR Measurement System and the sensor system including the adhesive pads for the attachment of the optical sensors to the body.

Documentation and Reporting of Adverse Events

AEs should be reported and documented in accordance with the procedures outlined below. The following data should be documented for each AE:

- Description/term of the symptom event (underlying diagnosis)
- Date of first occurrence and date of resolution (if applicable)
- Classification of "serious" or "not serious" (Section 7.1.2.2)
- Severity
- Causal relationship
- Action taken
- Outcome of event

For abnormal clinically significant laboratory findings, the clinical manifestation (diagnosis) should be noted as an adverse event (e.g. anemia instead of low hemoglobin). Should a clinically significant lab abnormality occur that is not part of a diagnosis, the abnormality itself may be reported as an AE. Laboratory abnormalities that meet the criteria for an AE should be followed until they have returned to normal or an adequate explanation of the abnormality is determined. When an abnormal laboratory result corresponds to a sign/symptom of an already reported AE it is not necessary to separately record the lab result as an additional AE.

Assessment of Severity

Each AE will be assigned a category by the investigator as follows:

- Mild: results in minimal transient impairment of a body function or damage to a body structure and/or does not require any intervention other than monitoring or OTC medication.
- Moderate: Results in moderate transient impairment of a body function or transient damage to a body structure and/or requires intervention, such as administration of medication or transfusion or laparoscopic or endoscopic procedure to prevent permanent impairment of a body function or damage to a body structure.

Severe: An event which is life threatening, results in permanent impairment of a body function or permanent damage to a body structure or necessitates significant intervention, such as major surgery, to prevent permanent impairment of a body function or permanent damage to a body structure. The term severe is often used to describe the intensity (severity) of a specific event (as in mild, moderate, or severe myocardial infarction); the event itself, however, may be of relatively minor medical significance (such as severe headache). This is not the same as serious, which is based on patient/event outcome or action criteria usually associated with events that pose a threat to a patient's life or functioning. Seriousness (not severity) serves as a guide for defining regulatory reporting obligations. An event that changes in severity (gets worse or gets better) should be noted as its worst severity.

Assessment of Causality

Every effort will be made by the investigator to assess the relationship of the AE, if any, to the study device (and components), investigational drug. Causality should be assessed using the categories presented below:

| Unrelated | Clinical event with an incompatible time relationship to study device or study drug, and that could be explained by underlying disease or other drugs or is incontrovertibly not related to the study device. |
|-----------|---|
| Unlikely | Clinical event whose time relationship to study device investigational drug makes a causal connection improbable, but that could plausibly be explained by underlying disease or other drugs. |
| Possible | Clinical event with a reasonable time relationship to study device or investigational drug, but that could also be explained by concurrent disease or other drugs. |
| Probable | Clinical event with a reasonable time relationship to study device or investigational drug and is unlikely to be attributed to concurrent disease or other drugs. |

Very Likely/Certain Clinical event with plausible time relationship to study device or investigational drug, and that cannot be explained by concurrent disease or other drugs.

AEs that are deemed related should be further assessed to determine if a relationship to the investigational drug, or device can be elucidated.

Action Taken

The investigator will describe the action taken in the appropriate section of the eCRF, as follows:

- None
- Concomitant interventional treatment(s) administered (includes medications or procedures)
- Other, specify

Outcome of the Event

The investigator will describe the outcome of the event in the appropriate section of the eCRF, as follows:

- Unknown
- Resolved
- Ongoing
- Resolved with sequelae
- Death (with date and cause reported)

Follow-up of Adverse Events

Subjects with AEs should be followed until the event is resolved or until, in the opinion of the investigator and medical monitor, the event is stabilized or determined to be chronic.

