7.1.2.2 Serious Adverse Events

Serious Adverse Event Definition

An SAE is any AE from this study that results in one of the following outcomes:

An adverse event that:

- a) led to death;
- b) led to serious deterioration in the health or the subject, that either resulted in:
 - 1) a life threatening illness or injury or
 - 2) a permanent impairment of a body structure or a body function, or
 - 3) in-patient or prolonged hospitalization, or
 - 4) medical or surgical intervention to prevent life-threatening illness or
 - injury or permanent impairment to a body structure or a body function;
- c) led to fetal distress, fetal death or a congenital abnormality or birth defect
Reporting requirements for all SAEs is detailed in Section 7.1.2.3.

Note: Planned hospitalization for a pre-existing condition, or a procedure required by the protocol without serious deterioration in health, is not considered a serious adverse event.

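### The Severe adverse-event grade has no intensity criterion, although its own explanatory text says severity means intensity, so intense but transient non-serious events cannot be graded above Moderate

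*Combined protocol and SAP*

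**What the plan says.** Section 7.1.2.1 (Assessment of Severity) has the investigator place each adverse event in one of three categories.

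- **Mild**: minimal transient impairment or damage, and/or an event that "does not require any intervention other than monitoring or OTC medication".
- **Moderate**: moderate transient impairment or transient damage, and/or a need for intervention. The examples are medication, transfusion, and laparoscopic or endoscopic procedures, tied to preventing permanent impairment or damage.
- **Severe**: "An event which is life threatening, results in permanent impairment of a body function or permanent damage to a body structure", or an event that "necessitates significant intervention, such as major surgery, to prevent permanent impairment of a body function or permanent damage to a body structure".

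The text under Severe then explains that the word describes how intense an event is, and that "the event itself, however, may be of relatively minor medical significance (such as severe headache"). It adds that this differs from serious, which rests on outcome or action criteria. An event whose severity changes is recorded at its worst grade.

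Section 7.1.2.2 defines SAEs. Section 9.6.1 summarises treatment-emergent events at event level by system organ class, preferred term and severity. Safety and tolerability are stated objectives in section 4.

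**The concern.** The definition of Severe and the explanation attached to it describe different things. The definition uses outcome and action criteria, which the explanation assigns to seriousness. The explanation gives severe headache as an example, and an ordinary severe headache meets no part of the definition.

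What is at stake is the meaning of the severity summary. The reactions that the protocol leads one to expect are mostly transient and non-serious: dizziness, vasovagal reaction and adhesive reactions (sections 8.1 to 8.2.1), and pain or burning with extravasation (section 8.3.1). If intensity cannot move such an event into the Severe row, an empty row says little about how well subjects tolerated the drug and the device. Investigators at up to 10 sites in two countries could also resolve the conflict differently, some following the definition and others the headache example.

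**Working it through.** No arithmetic applies. The check sets the definitions side by side and then runs the protocol's own example through the scale.

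**Step 1: which grades contain a degree-of-impairment criterion?**

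| Grade | Degree of transient impairment | Treatment or outcome criterion |
|---|---|---|
| Mild | Yes (minimal) | At most monitoring or over-the-counter medication |
| Moderate | Yes (moderate) | Intervention to prevent permanent impairment or damage |
| Severe | None | Life threatening; permanent impairment or damage; significant intervention to prevent these |

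The gradient stops at Moderate. Marked but transient impairment has no grade of its own.

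**Step 2: compare Severe with the SAE definition in section 7.1.2.2.**

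| Part of Severe (7.1.2.1) | Closest SAE criterion (7.1.2.2) |
|---|---|
| Life threatening | b(1): "a life threatening illness or injury or" |
| Permanent impairment or damage | b(2): "a permanent impairment of a body structure or a body function" |
| Significant intervention to prevent permanent harm | b(4): "medical or surgical intervention to prevent life-threatening illness or" injury or permanent impairment |

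All 3 parts of Severe have a close counterpart among the SAE criteria, and 0 of 3 describe intensity. The overlap is large but not exact:

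- SAEs also include in-patient or prolonged hospitalization (b(3)) and fetal or congenital events (c).
- b(4) covers any medical or surgical intervention for the stated purpose, including lesser ones that the severity scale places under Moderate.
- The criteria under b apply only where there is serious deterioration in health, whereas Severe asks only for permanent damage. A trivial permanent skin mark could therefore be Severe and not serious. It would reach that grade by permanence, not by intensity.

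**Step 3: grade an intense, self-limiting headache.** It is not life threatening, leaves nothing permanent and needs no major intervention.

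- Severe: none of the three parts is met.
- Moderate: this is the nearest fit on degree of impairment, although the impairment is more than moderate.
- Mild: the impairment is not minimal. But the criteria are joined by and/or, so the event also qualifies if monitoring or over-the-counter medication is enough.

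The highest grade available is Moderate, and a literal reader can justify Mild. The worst-grade rule does not help, because the worst grade available is still Moderate.

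**Step 4: look for a remedy elsewhere.** No other section of the protocol gives an intensity scale, and section 9.6.1 uses the grade without redefining it.

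**The case against.** The strongest reply is that this is a wording problem with little consequence. The headache remark is a general caution against confusing severe with serious, and the listed categories remain the operative rule. The prediction that sites will differ is not demonstrated. The protocol provides for site training and EDC completion guidelines, whose content is not visible and might settle the question. Seriousness, action taken and outcome are recorded separately for each event. Severity is only one of several event summaries, and no comparator arm or stated decision rule depends on it.

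Much of this stands. It limits the importance of the point, and divergence between sites is a risk, not a finding. But if the categories are the operative rule, Step 3 applies in full: intense transient events stop at Moderate.

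Three stronger readings are tempting, and the documents support none of them.

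- A reader might infer that the grade depends only on treatment and permanence. It does not, because degree of impairment separates Mild from Moderate.
- A reader might infer that the Severe row merely repeats the SAE table, so that no SAEs means no severe events. Step 2 shows mismatches in both directions.
- A reader might take the Pilot 2 results in section 8.1 (31 mild + 9 moderate = 40 events, none severe, no SAEs) as the scale's effect in action. The documents do not say which scale Pilot 2 used, so the counts neither support nor weaken the point.

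**Conclusion.** The point holds: the definition of Severe contradicts its own explanatory text, and the scale has no place for marked transient impairment. Read literally, a non-serious event cannot reach Severe through intensity, so the Severe row in the section 9.6.1 summary cannot inform the reader about intense non-serious events.

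This rests on investigators applying the definitions as written. If some follow the headache example instead, the grades become inconsistent, and the row is still not a dependable measure of intensity. The number of events affected cannot be derived, and no instance of a downgraded event is documented. SAE reporting runs on seriousness and is untouched, as are the P30 endpoint and the success criterion. This should be corrected, but it does not threaten the study's main conclusion.

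**What to change.** Reconcile the definition with its explanation in section 7.1.2.1 by two additions.

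1. Extend the existing gradient, so that Severe includes marked or severe transient impairment of a body function.
2. State that when the and/or criteria point to different grades, the degree of impairment decides, not the treatment given.

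Seriousness, action taken and outcome stay in their own fields, so no information is lost. Replacing the whole scale with one based on interference with usual activity is not needed. Laboratory, ECG and skin findings fit such a scale poorly, and the present impairment-and-damage wording can grade them.

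The cost is a protocol wording change, eCRF guidance and a training note. Some events will be graded higher than under the current text, and exact comparability with the pilot studies may be lost. If events have already been graded when the wording changes, the report should say which wording applied to them.

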7.1.2.2 Serious Adverse Events

Serious Adverse Event Definition

An SAE is any AE from this study that results in one of the following outcomes:

An adverse event that:

- a) led to death;
- b) led to serious deterioration in the health or the subject, that either resulted in:
 - 1) a life threatening illness or injury or
 - 2) a permanent impairment of a body structure or a body function, or
 - 3) in-patient or prolonged hospitalization, or
 - 4) medical or surgical intervention to prevent life-threatening illness or
 - injury or permanent impairment to a body structure or a body function;
- c) led to fetal distress, fetal death or a congenital abnormality or birth defect
Reporting requirements for all SAEs is detailed in Section 7.1.2.3.

Note: Planned hospitalization for a pre-existing condition, or a procedure required by the protocol without serious deterioration in health, is not considered a serious adverse event.

7.1.2.3 Reporting of Serious Adverse Events

Any SAE must be reported by the investigator if it occurs during the clinical study whether or not the event is considered to be related to the MediBeacon[®] Transdermal GFR Measurement System, or the investigational drug. All serious adverse events must be reported by the Investigator (or designee) by submitting the Serious Adverse Event Report Form (via the electronic data capture (EDC) system) or via email to MediBeacon within 24 hours of learning of the adverse event.

The Sponsor safety team, in cooperation with the Investigator, will assess all serious adverse events considered drug or device-related for potential reportability to regulatory authorities and ethical committees as an Unanticipated Adverse Device Effect (UADE) or as an expedited serious adverse event.

Note: It is also the responsibility of the Investigator to inform their Independent Ethics Committee (IEC) of other serious adverse events (i.e. non-UADEs) as required by their IEC procedures and in conformance with regulations.

SAEs must be reported within 24 hours of knowledge.

For submission of Serious Adverse Event information or Unanticipated Adverse Device Effects, the following email maybe used:

Email: [contact]

The investigator should not wait to receive additional information to document fully the event before notification to the Sponsor of an SAE, though additional information may be requested. Where applicable, information from relevant laboratory results, hospital case records, and autopsy reports should be obtained.

Instances of death, congenital abnormality, or an event that is of such clinical concern as to influence the overall assessment of safety, if brought to the attention of the investigator at any time and linked by the investigator to this study, should be reported to MediBeacon.

The sponsor or designee will promptly notify all relevant investigators and the regulatory authorities of findings that could adversely affect the safety of subjects, impact on the conduct of the study or alter the IEC approval/favorable opinion of the study. In addition, the sponsor, will expedite the reporting to all concerned investigators, to the IECs, and to the regulatory authorities of all adverse device reactions that are both serious and unanticipated.

